### **10.3.2 Statistical model, and method of analysis**

Analyses of the change from baseline in NT-proBNP and echocardiographic parameter was performed using an analysis-of-covariance model adjusted for baseline values. Logarithmic transformation is used for NT-proBNP, due to its skewed distribution.

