## Protocol synopsis

**Protocol title:** Angiotensin receptor-neprilysin inhibitor (ARNI, Sacubitril/Valsartan) versus Enalapril in patients with acute anterior wall ST-elevation myocardial infarction after emergency PCI: a prospective randomized trial

**Rationale & background information:** Ventricular remodeling after acute myocardial infarction (AMI) is closely related to the occurrence of heart failure (HF). Despite opening the infarct-related artery as early as possible and using the best medical treatment, about 41.5% of STEMI patients still have ventricular remodeling at 6 months. LV remodeling is a complex pathophysiological process that develops gradually over time. Neuroendocrine hormones, persistently activated, play an important role in this process, except for the extent of initial myocardial injury, and are closely associated with the progression of heart failure (HF).

In recent years, the application of Sacubitril/Valsartan (Sac/Val) has brought bright sight to patients with heart failure. Sac/Val can inhibit the activation of endorphinase and renin-angiotensin-aldosterone system (RAAS) at the same time. According to PARADIGM-HF study and other researches, Sac/Val could reduce cardiovascular mortality and re-admission rate of heart failure patients who had a reduced heart ejection fraction. Whether the initiation of Sac/Val immediately is effective and safe among patients with acute anterior STEMI (a high-risk factor for HF) is unknown. Therefore, the purpose of this study is to evaluate the safety and effectiveness of immediate initiation of Sac/Val in patients with acute anterior STEMI after PCI.

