**Table 7-1 Assessment schedule**

phase	screening	Randomization	Outpatient dose titration period						Follow-up period											
			1	2	3a	3b	3c	3d	4a	4b	4c	4d	4e							
Visit	D/S*																			
Weeks (w)			-2 to -1w	-1W to -0	2w	4w	6w	8w	10w	12w	16w	20w	24w(EOS)							
Informed consent form	S	x																		
Inclusion/Exclusion criteria 	DS	x 2	(x)																	
Demography/Medical history (including smoking history)	DS	x																		
Cardiovascular disease History	DS	x																		
Diabetes mellitus History	DS	x																		
Physical Exam 	S	x		x	(x)	x	x	x	x	x	x	x	x	x	x	x	x	x	x	x
Height (H) / Weight (W)	DS	H / W		W	W	W	W	W	W	W	W	W	W	W	W	W	W	W	W	W
Vital signs	DS	x	x	x	x	x	x	x	x	x	x	x	x	x	x	x	x	x	x	x
Waist/hip circumference	DS			x																
Onset to balloon, h	DS	x																		
KILLIP Classification	DS	x																		
TIMI flow grade	DS	x																		
Coronary heart disease and CV Medications	DS	x	x	x	x	x	x	x	x	x	x	x	x	x	x	x	x	x	x	x
Concomitant Medications	DS	x	x	x	x	x	x	x	x	x	x	x	x	x	x	x	x	x	x	x
Endpoint information	DS	x	x	x	x	x	x	x	x	x	x	x	x	x	x	x	x	x	x	x
AEs / SAEs	DS	x	(x)	x	x	x	x	x	x	x	x	x	x	x	x	x	x	x	x	x

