**Table 7-2 Routine laboratory examinations**

Hematology*	Biochemistry*	Urine measurements
Red Blood Cells count White Blood Cells count Platelet Count Hemoglobin Hematocrit WBC Differential	Sodium Potassium Chloride Calcium Blood urea nitrogen (BUN) Creatinine Total Bilirubin Aspartate amino-transferase (AST) Alanine amino-transferase (ALT) Alkaline phosphatase Total protein Albumin Uric Acid Serum Pregnancy Testa Lipid profile (total cholesterol, LDL, HDL, and triglycerides) Hemoglobin A1C	UACR (to calculate urinary albumin/creatinine ratio) Urinalysis

	High Sensitivity Cardiac Troponin I (Hs-cTnI)	
--	--	--

\* List of laboratory assessments performed at Visits 1, 2, 3, 4.

a. At Visit 1 and in case of positive urine pregnancy test only.

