### **10.2 Patient demographics/other baseline characteristics**

Baseline value is defined as the last non-missing assessment prior to the first dose of randomized study medication unless specified otherwise. Summary statistics will be provided by treatment group for demographics and baseline characteristics, including age, sex, weight, height, body mass index (BMI), Previous history of hypertension, prior history of Diabetes mellitus, Previous smoking history, Killip class, blood tests, Number of diseased vessels, vital signs, etc. BMI will be calculated as  $\text{weight (kg)} / \text{height}^2 \text{ (m}^2\text{)}$  from the collected height and weight at Visit 1 (Screening Visit). Continuous variables will be summarized using n, mean, standard deviation, geometric mean and 95% confidence interval. Categorical variables will be summarized using frequency and percentage.

The difference between treatment groups will be compared using the Fisher's exact test for categorical variables or using t-test or Mann-Whitney U test for continuous variables. The p-values will be provided for descriptive purposes and will not be considered to define any formal basis for determining factors to be included in statistical models.

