### **10.4.2 Statistical model, and method of analysis**

The secondary efficacy variables will be analyzed using Kaplan-Meier estimates and Cox proportional hazards models. The hazard ratios, 95% confidence intervals, and two-sided P values are calculated using the model to adjust the following baseline prognostic factors: Age, gender, body mass index, total cholesterol, triglycerides, history of hypertension, diabetes and Previous smoking.

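### The four primary ANCOVAs adjust for baseline values only, although markers of the initial infarct injury are already collected before randomization: a missed precision gain of unknown size, not an error

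*Protocol*

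**What the plan says.** Section 10.3.2 of the protocol, repeated in the synopsis under data analysis, states that change from baseline in NT-proBNP (log scale) and in the echocardiographic parameters is "performed using an analysis-of-covariance model adjusted for baseline values". No further covariate is named. Section 10.2 defines baseline as the "last non-missing assessment prior to the first dose of randomized study medication".

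The background part of the synopsis says that persistently activated neuroendocrine hormones matter for remodelling, "except for the extent of initial myocardial injury". The English is awkward, but the natural reading is that initial injury is a driver alongside the hormones.

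Table 7-1 records "Onset to balloon, h", "KILLIP Classification" and "TIMI flow grade" at screening. Table 7-2 and section 7.5.4.2 have hs-cTnI measured at Visits 1 to 4, and Visit 1 precedes randomization.

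For the secondary composite, section 10.4.2 does list adjustment factors for the Cox model: "Age, gender, body mass index, total cholesterol, triglycerides, history of hypertension, diabetes and Previous smoking". None of these eight is a marker of infarct injury.

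**The concern.** The protocol names a driver of the outcome and measures several markers of it before treatment assignment, but leaves them out of the primary model. Any part of the change in LVEF, volumes or NT-proBNP that these markers predict beyond the outcome's own baseline stays in the error term. That makes the confidence interval wider than it need be.

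The sample size leaves little slack. The planned number gives almost exactly 80% power for LVEF, so even a modest precision gain would be useful, and this one needs no extra patients or procedures. Pre-specification also matters: covariates added after an imbalance has been seen are open to challenge.

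**Working it through.** **Inputs from the protocol (section 10.6).** LVEF difference 3 points, SD 6 points, α = 0.05, power 80%, 1:1 allocation, 64 per group, 10% attrition, total 142. Sidedness is not stated; the two-sided calculation reproduces the figure.

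**Reproducing the plan's own figure.** Two-sample t-test, two-sided 0.05, noncentral t: 64 per arm (63 by the normal approximation; a one-sided test would give 50). With attrition, 128 / 0.9 = 142.2, against the stated 142. Working back, 142 × 0.9 / 2 = 63.9 evaluable per arm. Power at 64 per arm is 80.1%.

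**Effect of adding injury markers.** Let R² be the share of residual variance that the markers explain beyond own baseline. The protocol gives no value, so a range is assumed. It is also assumed that 6 is the residual SD of the own-baseline model and that 64 per arm are analysed.

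- Residual SD = 6 × √(1 − R²)
- Noncentrality = 3 / (SD × √(2/64))
- 95% interval half-width = 1.96 × SD × √(2/64)
- Power from the noncentral t. Charging three or four extra degrees of freedom gives the same powers to the first decimal.

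| Assumed R² | Residual SD | Power | Half-width (LVEF points) |
|---|---|---|---|
| 0 | 6.00 | 80.1% | 2.08 |
| 0.02 | 5.94 | 80.9% | 2.06 |
| 0.05 | 5.85 | 82.1% | 2.03 |
| 0.10 | 5.69 | 84.1% | 1.97 |
| 0.20 | 5.37 | 88.0% | 1.86 |

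The gain is about one to two power points at the low end and about eight at the top of the assumed range.

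**Chance imbalance.** With 64 per arm, the standardized difference between arms in any one factor has SD √(2/64) = 0.177. If that factor explains 5% of residual variance, the typical shift in the LVEF estimate is 0.177 × √0.05 × 6 ≈ 0.24 points. The standard error of the difference is 6 × 0.177 ≈ 1.06 points and already contains this shift. It is the same variance as in the table, seen from another side, and must not be counted twice.

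**The case against.** The strongest reply is that nothing here is wrong. ANCOVA on change, adjusted for the outcome's own baseline, is a standard, unbiased analysis under 1:1 randomization, and a longer covariate list is often left to the SAP. That stands, and it is why the point is an improvement and not a correction. Still, section 10.3.2 states the model without deferring to another document, and section 10.4.2 shows that this protocol does fix covariates where it wants them.

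Several further objections limit the size of the point:

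- **Overlap with own baseline.** The baseline echocardiogram is taken after PCI (section 7.4.5), so baseline LVEF, volumes and NT-proBNP already carry injury information. Entry is also restricted to anterior STEMI without previous infarction, chronic heart failure or PCI. A low partial R² is quite possible.
- **Meaning of the SD.** Section 10.6 does not say whether 6 is the raw SD of change or a residual SD. If it is raw, the planned baseline adjustment may already lift power above 80%.
- **Quality of the troponin value.** Sampling time after the infarct may vary between patients, which weakens hs-cTnI as a measure of infarct size.

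A reader might also infer three stronger claims that the documents do not support. The first is that imbalance in injury markers biases the primary estimates; it does not, because randomization makes it chance variation that the standard error covers. The second is that baseline measurements are spread widely over time after the infarct. Table 7-1 gives visit windows and, as extracted, has no echocardiography or NT-proBNP row, so this spread is inferred and cannot be quantified. The third is that the Cox model's eight factors make the protocol inconsistent. They do not: a different outcome may have different covariates, and none of the eight is an injury marker anyway.

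**Conclusion.** The point holds as a missed precision gain. The primary model names baseline values only, the protocol's own rationale gives weight to the initial injury, and suitable pre-randomization markers are already collected. The stated analysis remains valid and unbiased, and the sample size calculation reproduces.

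The size is unknown because the protocol gives no partial R². Taking 6 as the residual SD and 64 analysed per arm, LVEF power would move from about 80.1% to between 80.9% (2% further variance explained) and 88% (20%). These figures concern LVEF only; no comparable inputs are given for NT-proBNP or the volumes. The change is worth making because it is nearly free, not because the current plan fails.

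**What to change.** In section 10.3.2 and the synopsis, pre-specify for all four primary variables an ANCOVA with:

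- the outcome's own baseline;
- log onset-to-balloon time;
- Killip class (I versus II or higher);
- log hs-cTnI from the Visit 1 sample.

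The added markers should be measured at or before randomization. For troponin the Visit 1 sample should be named explicitly, in place of the general last-before-first-dose rule in section 10.2. Section 4.2.2 applies the 36-hour washout only to patients assigned to sacubitril/valsartan, so the first randomized dose comes later in that arm. A last pre-dose troponin could then be sampled at systematically different times in the two arms.

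TIMI flow can be left out to keep the list short; Table 7-1 does not say whether the grade is from before or after PCI. Keep the baseline-only model as a sensitivity analysis.

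The cost is a change of analysis wording, about three degrees of freedom out of roughly 128, and a simple stated rule for a missing covariate value so that no randomized patient is dropped for that reason. No new data, visits or patients are needed.

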## **10.4 Analysis of secondary objectives**

### **10.4.1 Secondary efficacy variables**

The secondary efficacy variable is a composite of death, reinfarction, outpatient HF or HF hospitalization, arrhythmia, and stroke.

### **10.4.2 Statistical model, and method of analysis**

The secondary efficacy variables will be analyzed using Kaplan-Meier estimates and Cox proportional hazards models. The hazard ratios, 95% confidence intervals, and two-sided P values are calculated using the model to adjust the following baseline prognostic factors: Age, gender, body mass index, total cholesterol, triglycerides, history of hypertension, diabetes and Previous smoking.

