### **4.1 Justification of key elements of the study design**

#### **4.1.1 Selection of the primary endpoint**

We chose NT-proBNP as the primary endpoint in this study because natriuretic peptide concentrations are associated with adverse outcomes in patients with AMI. Although both ANP and BNP undergo degradation by neprilysin, the biologically inert NTproBNP, cleaved from proBNP along with BNP, is not a substrate for neprilysin degradation, and changes in this marker still reflect reduction in left ventricular wall stress even in the setting of neprilysin inhibition.

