#### **7.4.4 Biomarkers**

Biomarker measurements will be obtained from serum and plasma in a subset of patients at selected sites before surgery and at Visits 1, 2, 3 and 4 to determine effects of treatments on biomarkers of STEMI after PCI.

Biomarkers studied include:

NT-proBNP

Details on sample collection, handling and shipment of biomarker samples will be provided to investigators in the laboratory manual.

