#### **7.4.5 Cardiac ultrasonic parameters**

Professionals use Philips IE33 ultrasound system (Philips Medical System, Bothell, Washington, USA) for echocardiographic measurements after PCI and 12 and 24 weeks after discharge. Use the biplane Simpson method to measure LVEDV, LVESV and LVEF in the apical four-chamber heart and two-chamber heart views according to

the recommendations issued by the American Society of Echocardiography and the European Cardiovascular Imaging Association.

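### The Cox model for the secondary composite includes no measure of baseline cardiac severity, although baseline NT-proBNP and LVEF are needed for the primary analysis; the cost is precision and power, not validity.

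*Protocol*

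**What the plan says.** Section 10.4.2 analyses the composite of death, reinfarction, heart failure, arrhythmia and stroke with Kaplan-Meier estimates and a Cox model, "using the model to adjust the following baseline prognostic factors": "Age, gender, body mass index, total cholesterol, triglycerides, history of hypertension, diabetes and Previous smoking". The data analysis part of the synopsis gives the same list.

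Other sections bear on that list:

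- Section 4.1.1 justifies NT-proBNP as an endpoint because "natriuretic peptide concentrations are associated with adverse outcomes in patients with AMI".
- Section 10.3.2 analyses the primary outcomes, NT-proBNP and the echocardiographic parameters, with an "analysis-of-covariance model adjusted for baseline values". Baseline NT-proBNP and baseline LVEF must therefore exist for that analysis.
- Section 7.4.5 schedules "echocardiographic measurements after PCI and 12 and 24 weeks after discharge", which supplies baseline LVEF.
- Section 7.4.4 takes biomarkers, of which NT-proBNP is the only one listed, "in a subset of patients at selected sites before surgery and at Visits 1, 2, 3 and 4".
- Table 7-1 lists "KILLIP Classification" at screening, and section 10.2 summarises "Killip class, blood tests, Number of diseased vessels, vital signs" at baseline.
- Section 6.3 names no stratification factor. Section 10.2 says that baseline p-values will not decide which factors enter the models.

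**The concern.** The protocol calls the eight listed factors prognostic, but they are demographic, metabolic and history variables. The composite counts events over about 24 weeks after an anterior infarct and includes heart failure treated in or out of hospital. The one marker that the protocol itself links to adverse outcomes after infarction, NT-proBNP, is not in the model for those outcomes. LVEF, which drives the sample size, is also absent.

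Omitting a prognostic covariate from a Cox model has two effects. The treatment hazard ratio moves toward 1 relative to the one conditional on that covariate, and power falls. A chance difference between arms in that covariate also stays in the estimate as noise. With no stratification factor named, the prespecified list is the only stated means of adjusting for such a difference. At stake is the efficiency of the secondary analysis and the reading of its hazard ratio.

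**Working it through.** **The plan's own figure.** Section 10.6 assumes an LVEF difference of 3 with SD 6, alpha 0.05, power 80% and 1:1 allocation. A two-sided two-sample t-test needs 63.8, so 64 per arm, as stated. Allowing for 10% loss, 128 / 0.90 = 142.2, against the stated 142, or 71 per arm. The protocol gives no event rate, hazard ratio or power for the composite, so there is no Cox figure to reproduce. Everything below rests on assumed values.

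**Chance imbalance.** With 71 per arm, the standardised difference in any one baseline covariate has SD sqrt(2/71) = 0.168. The probability that it exceeds 0.2 in absolute value is 2 × (1 − Φ(0.2/0.168)) = 23%. If a severity score had a hazard ratio of 2.0 per SD (assumption), leaving it out would shift the treatment hazard ratio by about:

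- 2.0^0.168 = 1.12 for an imbalance of one chance SD;
- 2.0^(1.96 × 0.168) = 1.26 for an imbalance reached or exceeded one time in 20.

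**Power gain from a two-for-two swap.** This was simulated with 142 patients, exponential times, a conditional treatment hazard ratio of 0.5, eight covariates plus treatment, two-sided 0.05 and 600 trials per scenario. Two covariates with no prognostic value were replaced by two prognostic ones. The Monte Carlo standard error is about sqrt(0.4 × 0.6/600) = 2 points.

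| Combined hazard ratio per SD (assumed) | About 27 events | About 45 events |
|---|---|---|
| 1.5 | 41% to 41% | 57% to 59% |
| 2.0 | 39% to 41% | 58% to 65% |
| 2.5 | 36% to 43% | 53% to 62% |

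The gains are 0, 2 and 7 points at about 27 events, and 2, 7 and 9 points at about 45. These counts are event proportions of 27/142 = 19% and 45/142 = 32%.

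**A second simulation, with wider assumptions.** Here three independent prognostic factors are omitted, the eight listed ones have a hazard ratio of 1.1 per SD each, and there are 800 runs per scenario. The table gives power with the listed eight, then with a five-covariate model (the three omitted factors plus two listed ones).

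| Hazard ratio per SD, each omitted factor | 15% events | 30% events | 45% events |
|---|---|---|---|
| 1.3 | 31% to 31% | 56% to 58% | 72% to 74% |
| 1.6 | 30% to 33% | 49% to 60% | 65% to 75% |
| 2.0 | 26% to 32% | 39% to 55% | 50% to 77% |

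At 30% events and 2.0 per SD, the median estimate with the listed eight was 0.57 against a true conditional 0.50. With the five-covariate model it was 0.50.

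Three independent factors at 2.0 each combine to exp(0.693 × sqrt(3)) = 3.3 per SD, so the bottom row is an extreme case.

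**Validity.** With a true hazard ratio of 1, the listed-eight model rejected in 4% to 6% of runs. The five-covariate model also rejected in about 4% to 6%. Adding all three factors to the eight raised rejection to as much as 8.1% (15% events, 2.0 per SD). This favours replacing covariates over adding them. The planned model already has 9 parameters, which is 27/9 = 3 to 45/9 = 5 events per parameter at the assumed counts.

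**The case against.** The strongest reply is that nothing here is invalid. The list is prespecified, the test holds its level, and chance imbalance is already part of the hazard ratio's sampling error. That stands. A reader might infer that the planned hazard ratio is biased or that the type I error is inflated. The documents and the calculations support neither. The movement toward 1 reflects non-collapsibility, that is, a different and less conditional hazard ratio.

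The gains are also modest. At about 27 events, two of the three are within Monte Carlo error. The largest gain, 27 points in the second simulation, needs 45% events and three independent, strong factors. NT-proBNP, LVEF and Killip class overlap as measures of pump function, so independence overstates the gain. That stands too.

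A reader might infer that the omitted factors are strong and the listed ones weak. The protocol supports only an association for NT-proBNP and does not grade it; strength for LVEF and Killip class is assumed. Excluding prior infarction and chronic heart failure may narrow their range. Lipids may plausibly matter for reinfarction and stroke.

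A reader might also take the replacement data as certainly available. Section 7.4.4, read literally, confines NT-proBNP to a subset, and a complete-case model would then lose patients and events. This qualifies the remedy but does not defeat it. Section 10.3.1 makes NT-proBNP a primary outcome and section 10.1 analyses all randomised patients, so section 7.4.4 needs reconciling anyway. LVEF can be swapped in regardless.

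Finally, neither simulation tests Killip class as such. As a multi-level category in place of BMI it could add parameters, so it is not part of the main recommendation.

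**Conclusion.** The point holds as an inexpensive improvement to a secondary analysis. The eight fixed covariates contain no measure of baseline cardiac severity, although the protocol links natriuretic peptides to outcome after infarction and needs baseline NT-proBNP and LVEF for its primary analysis. The result is some loss of precision and power, and a hazard ratio nearer 1 than the severity-adjusted one.

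For a two-for-two swap the gain is about 0 to 7 points of power at about 27 events and 2 to 9 points at about 45. These figures assume a conditional hazard ratio of 0.5, a combined prognostic hazard ratio of 1.5 to 2.5 per SD, and no prognostic value in the replaced covariates. With few events or weak factors the gain is near zero. Better adjustment does not make the composite well powered: by Schoenfeld's formula, 80% power at a hazard ratio of 0.5 needs 4 × (1.960 + 0.842)² / (ln 0.5)² = 65.3, so 66 events among 142 patients.

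**What to change.** Before unblinding, in section 10.4.2 and the synopsis:

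1. Replace total cholesterol and triglycerides with baseline log NT-proBNP and baseline LVEF, using the baseline definition in section 10.2. The model stays at eight covariates.
2. Report the present eight-factor list as a sensitivity analysis.
3. Treat Killip class as optional. If it is used, enter it as a single binary or ordinal term in place of a listed covariate, not in addition.
4. Reconcile section 7.4.4 with sections 10.1 and 10.3.1, so that it is clear whether baseline NT-proBNP is taken in every randomised patient.
5. Prespecify a simple imputation for a missing baseline NT-proBNP or LVEF.

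The cost is analysis wording plus the correction of section 7.4.4. If NT-proBNP is sampled in all patients, as its primary role implies, no new measurement is needed. The downsides are the imputation rule and that adjustment for lipids moves to the sensitivity analysis.
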